#### **5.3.1.2. Peramivir Safety**

Safety of various doses of peramivir in acute uncomplicated influenza has been evaluated in 1453 adults. The most frequently observed treatment emergent AEs (TEAEs) across all adult subjects with acute uncomplicated influenza treated with various doses of peramivir were diarrhea (7.4%), decreased neutrophil count (5.5%), and increased blood glucose (5.0%). The only events reported in  $\geq 2\%$  of subjects treated with peramivir 600 mg and for which the rate was greater than placebo were diarrhea (7.6% vs. placebo 7.0%), decreased neutrophil count (5.7% vs. placebo 0.0%), hyperglycemia (5.3% vs. placebo 4.8%) and urine leukocytes (2.8% vs. placebo 1.8%). Adverse event (AE) rates overall were similar to placebo and oseltamivir. No safety signals have emerged from these trials.

#### 5.4. Rationale for Study

There is disagreement on the degree of benefit risk provided by NAIs. A 2012 systematic meta-analysis (Hsu, Santesso et al. 2012) supports the conclusion that early treatment with neuraminidase inhibitors such as oseltamivir is associated with reduced mortality and reduced rates of hospital admission. Another independent meta-analysis of 11 randomized clinical trials also found that oseltamivir reduced the risk of lower respiratory tract complications and the use of antibiotics (Hernan and Lipsitch 2011). Mortality benefits were supported by a meta-analysis of hospitalized patients with H1N1 pandemic influenza, although the benefit was not seen in children (Muthuri, Venkatesan et al. 2014). This is in contrast to 2 Cochran reviews, one reviewing both oseltamivir and zanamivir (Jefferson, Jones et al. 2009) and a more recent review focused on oseltamivir (Jefferson, Jones et al. 2014), that found only modest efficacy as measured by time to alleviation of symptoms and no reduction in lower respiratory tract complications. The 2014 review indicated that while there was modest efficacy in healthy adults and children, children with asthma did not benefit. There was no change in the hospital admission rate for adults and insufficient data in children. While oseltamivir did appear to reduce the incidence of unverified pneumonia in adults, there was no decrease in the incidence for children. The review also asserted that there was no decrease in the common complications of influenza such as bronchitis, otitis media and sinusitis.

The CDC responded (CDC 2014) by reiterating their recommendation of the use of antiviral treatment of patients with influenza in certain populations.

The CDC recommendation is as follows:

Antiviral treatment is recommended as early as possible for any patient with confirmed or suspected influenza who is hospitalized; has severe, complicated, or progressive illness; or is at higher risk for influenza complications. Persons at higher risk for influenza complications recommended for antiviral treatment include: children aged younger than 2 years; adults aged 65 years and older; persons with chronic pulmonary (including asthma), cardiovascular (except hypertension alone), renal, hepatic, hematological (including sickle cell disease), metabolic disorders (including diabetes mellitus), or neurologic and neurodevelopment conditions (including disorders of the brain, spinal cord, peripheral nerve, and muscle such as cerebral palsy, epilepsy [seizure disorders], stroke, intellectual disability [mental retardation], moderate to severe developmental delay, muscular dystrophy, or spinal cord injury); persons with immunosuppression, including that caused by medications or by human immunodeficiency virus (HIV) infection; women who are pregnant or postpartum (within 2 weeks after delivery); persons aged younger than 19 years who are receiving long-term aspirin therapy; American Indians/Alaska Natives; persons who are morbidly obese (i.e., body-mass index is equal to or greater than 40); and residents of nursing homes and other chronic-care facilities.

It is apparent that the definitions of high risk in this context is empirical, and subject to further modifications as additional risk factors are identified in seasonal and pandemic influenza outbreaks.

There remains a significant unmet need for influenza therapies for patients who are specifically at an increased risk of complications. Peramivir has demonstrated efficacy and safety when used in acute uncomplicated influenza in adults in the general population. This study aims to develop additional data on the safety, pharmacokinetics and effectiveness of IV peramivir in patient groups that are at risk of complications from influenza. In particular, this study will target elderly adults ( $\geq 65$  years of age) as well as other groups at increased risk of complications (e.g., pregnant women, residents of long term care facilities, American Indians and Alaskan Natives) and adults with comorbidities that increase the risk of

complications (e.g., adults with asthma, heart disease, diabetes). A complete list of chronic health conditions is provided in the inclusion criteria in Section [8.1](#).

**6. TRIAL OBJECTIVES AND PURPOSE**

**6.1. Primary objective**

- To evaluate the safety and tolerability of peramivir administered intravenously in elderly subjects with acute uncomplicated influenza and in subjects with acute uncomplicated influenza who are at higher risk for influenza complications

**6.2. Secondary Objectives**

- To describe the pharmacokinetics of IV peramivir in elderly and high risk subjects with acute uncomplicated influenza.
- To evaluate the effectiveness of IV peramivir in elderly and high risk subjects with acute uncomplicated influenza.
- To evaluate the incidence of influenza complications, specifically otitis media, sinusitis, bronchitis or pneumonia requiring antibiotic use diagnosed after initiation of treatment

## **7. INVESTIGATIONAL PLAN**

### **7.1. Endpoints**

#### **7.1.1. Primary Endpoint**

The primary endpoint of this study will be safety and include the assessment of AEs, laboratory abnormalities (clinical chemistry, hematology and urinalysis), vital signs and physical examinations.

#### **7.1.2. Secondary Endpoints**

Secondary endpoints will include:

- Pharmacokinetic (PK) analyses
- Change (reduction) in influenza virus titer by  $\log_{10}$  TCID50/mL and by reverse transcriptase polymerase chain reaction (RT-PCR)
- Time to alleviation of clinical symptoms of influenza (per age appropriate symptoms).
- Time to resolution of fever
- Incidence of influenza-related complications
- Incidence of hospital admission post treatment
- Changes in viral shedding measured by quantitative viral titer assay (TCID50) and/or quantitative PCR
- Change in influenza virus susceptibility to neuraminidase inhibitors

### **7.2. Overall Study Design and Plan**

This is a multicenter, single-arm, open-label study to evaluate the safety, PK and effectiveness of a single dose of IV peramivir in elderly subjects ( $\geq 65$  years of age) with acute uncomplicated influenza and in subjects with acute uncomplicated influenza at higher risk for influenza complications.

A subject's duration of participation in this study is expected to be 14 days and will include up to 4 clinic visits. Following treatment on study Day 1, subjects will undergo follow-up assessments on Days 3, 7, and 14 in the clinic. Additional, unscheduled visits may be required for subjects who report symptoms of influenza of moderate or severe intensity at Day 14 or have persistent AEs and/or treatment-emergent laboratory findings that require medical monitoring or management.

### **7.3. Study Measurements and Visit Schedule**

The schedule of assessments for this study is presented in [Table 1](#).

**Table 1. BCX1812-306: Schedule of Assessments**

Assessments	Screening 	Baseline  (Pre-dose)	Day 1 Treatment Day 	Day 3	Day 7 (+ 2 days)	Day 14 (+ 3 days) / End of Study	Early Withdrawal
Informed Consent	X						
Inclusion/Exclusion Criteria	X						
Medical History/Physical Exam	X			X 	X 		
Vital Signs 	X			X	X	X	X
Body Temperature 	X	X	X	X	X	X	X
Clinical Chemistries and Hematology 		X			X		X
Urinalysis 		X			X		X
Pregnancy Test (Urine or Serum)	X					X	X
Assessment of influenza symptoms 	X		X	X	X	X	X
Ability to Perform Usual Daily Activities 		X		X	X	X	X
Influenza Related Complications (IRC) 	X			X 	X	X	X
Concomitant Medications Review	X		X	X	X	X	X
Subject Diary Review			X	X	X	X	X
Pharmacokinetic (PK) Sampling			X				
Serum sample for influenza antibody analysis 		X		X	X		X
Swabs for Virology Analysis		X		X	X		X
Rapid antigen test (RAT) or FDA- approved PCR test for influenza A and B on nasal specimen	X						

Assessments	Screening	Baseline (Pre-dose)	Day 1 Treatment Day	Day 3	Day 7 (+ 2 days)	Day 14 (+ 3 days) / End of Study	Early Withdrawal
Study Drug Administration			X				
Adverse Events 	X	X	X	X	X	X	X

- 1 It is expected that the date of Screening, Baseline, and Day 1 (date of study drug administration) will be the same. Day 1 consists of pre and post-dose assessments.
- 2 Vital sign measures will include blood pressure, pulse rate, and respiration rate. Vital signs will be recorded once during Screening, and vital signs will be taken once on remaining study visit days.
- 3 The investigator will record oral body temperature at Screening. Thereafter, the subject or care giver will record oral body temperature approximately every 12 hours in the Subject Diary until temperature normalizes for 48 hours (i.e. temperature without antipyretic is < 37.4°C/ 99.4°F orally for 4 measurements).
- 4 Clinical laboratory assessments performed at Screening are for the purpose of establishing a baseline. Subjects may be enrolled and begin treatment with study drug prior to receiving results. These labs may be done at any visit if necessary for patient management or adverse event monitoring purposes.
5. Influenza signs and symptoms will be recorded by the study personnel at Screening, then by the subject or care giver twice daily beginning on Day 1 through Day 13, and prior to the subject's clinic visit on Day 14 or until each symptom is 0 or 1 for 48 hours.
- 6 Perform a targeted physical exam on Day 3 and Day 7
- 7 If an influenza related complication (IRC) is suspected the subject will be instructed to return to the clinic as appropriate to confirm the presence or absence of IRCs.
- 8 A single serum specimen will be collected, where possible, pre-dose on Day 1, Day 3 and on Day 7 for analysis of influenza antibody titers.
- 9 Adverse events are to be collected from the time of informed consent through the follow-up period ending on Day 14.

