  - History of heart disease including myocardial infarction, angina requiring treatment, congestive heart failure requiring treatment, arrhythmia including atrial fibrillation and valvular dysfunction
  - History of blood dyscrasias including sickle cell anemia and thalassemia
  - History of renal impairment (creatinine clearance  $[\text{CrCl}] < 50$  mL/min as determined by the Cockcroft-Gault formula) including patients on dialysis
  - History of liver disease including cirrhosis
  - Mild to moderate immunocompromised, including: history of human immunodeficiency virus (HIV) disease on stable highly active antiretroviral therapy (HAART) with last known CD4+ count  $\geq 200$  cells/ $\mu\text{L}$ ; known neutropenia with ANC  $> 500$  cells/ $\mu\text{L}$ ; chronic corticosteroid use of  $< 20$  mg/d for any indication.
  - History of diabetes mellitus (Type I or II)
  - Morbid obesity (body mass index  $[\text{BMI}] \geq 40$ )
  - American Indian or Alaskan native
5. Written informed consent

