## 9. TREATMENT OF SUBJECTS

### 9.1. Study Drug Dose Rationale

Subjects will be dosed with peramivir at the dosage levels currently approved in the US package insert for peramivir. The standard dose will be a single IV dose of 600 mg for subjects with CrCL  $\geq$  50 ml/min and reduced for subjects with CrCL < 50 ml/min as described in Section 9.4.

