### 9.3. Study Drug Preparation and Administration

The Principal Investigator at each study center will designate a pharmacist (or other qualified study staff member) to prepare IV peramivir.

Subjects will receive a single dose of 600 mg peramivir (or less if renally impaired) diluted in 0.9% saline, 0.45% saline, 5% dextrose or lactated Ringer's using the technique described in a separate drug preparation instruction sheet, administered IV over a period of 15 to 30 minutes. The calendar date and 24-hour clock time (start and end of the IV infusion) will be recorded.

The intravenous line used to administer peramivir must be flushed prior to and after peramivir administration. No other medications should be administered through the same IV line during peramivir administration.

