Eligible subjects will be enrolled. The study pharmacist/designee will prepare an order for study drug as defined in Section 9.3 , which includes the subject's study number.

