#### **10.1.2. Treatment Period**

Randomization and study drug administration should begin as soon as possible following determination that the subject is eligible for enrollment at Screening. Therefore, it is anticipated that the date of Screening and Day 1 (date of administration of the first dose of study medication) will be the same day. Day 1 represents the first day of dosing.

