##### **10.1.2.1. Baseline (Pre-dose)/Day 1**

The following Baseline procedures/evaluations will be performed after Screening and prior to dosing on Day 1:

- Obtain a bilateral adequate nasal swab specimen for viral subtyping, culture, quantitative PCR assay and susceptibility to neuraminidase inhibitors.
- Obtain and record body temperature
- Blood and urine specimen collection for clinical chemistry and clinical hematology tests as specified in Sections 11.2.1 and 11.2.2 and a serum sample for future influenza antibody analysis.

Following completion of the baseline procedures administer study drug:

- Administer study drug (at hour 0) and record the calendar date and 24-hour clock time for the start and finish of the IV infusion.
- Obtain and record body temperature

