### **11.2. Clinical Laboratory Evaluations**

#### **11.2.1. Clinical Chemistry Profiles**

Clinical chemistry profiles will include a Chemistry 20 panel (includes sodium, potassium, chloride, total CO2 [bicarbonate], creatinine, glucose, urea nitrogen, albumin, total calcium, total magnesium, phosphorus, alkaline phosphatase, alanine aminotransferase (ALT), aspartate aminotransferase (AST), total bilirubin, direct bilirubin, lactate dehydrogenase (LDH), total protein, total creatine kinase, and uric acid).

Blood samples for clinical chemistry profiles will be collected at Screening and at Day 7 or early termination visit (if the early termination visit occurs prior to Day 7). Clinically significant results should be reported as AEs. If Day 7 clinical chemistry profiles are, in the opinion of the investigator, significantly abnormal or significantly changed from baseline at Day 7, they should be repeated at the Day 14 visit.

At screening, creatinine clearance will be calculated by the Cockcroft-Gault equation (using actual body weight and serum creatinine) (see Appendix 16.1).

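### The single dose depends on creatinine clearance, but the protocol allows dosing before laboratory results, gives no dose below 10 mL/min, and the SAP plans no table of dose against clearance

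*Protocol*

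**What the plan says.** **Dose rule.** Protocol 9.1 reads "The standard dose will be a single IV dose of 600 mg for subjects with CrCL" of at least 50 mL/min, with a reduction below that as set out in 9.4. Table 2 gives 600 mg at 50 mL/min or more, 200 mg at 30 to 49, and 100 mg at 10 to 29. It has no column below 10. Section 9.4 sends hemodialysis subjects to the same table, to be dosed after dialysis.

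**When clearance is known.** Section 11.2.1 says "At screening, creatinine clearance will be calculated by the Cockcroft-Gault equation", using actual body weight and serum creatinine. Footnote 4 to Table 1, attached to the chemistry/hematology and urinalysis rows, describes these tests as establishing a baseline and adds "Subjects may be enrolled and begin treatment with study drug prior to receiving results". SAP 1.2 carries the same footnote.

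**Sequence on Day 1.** Section 10.1.1 (Screening) ends with "The study pharmacist/designee will prepare an order for study drug as defined in Section 9.3", and 9.3 specifies "a single dose of 600 mg peramivir (or less if renally impaired"). Section 10.1.2 says "study drug administration should begin as soon as possible following determination that the subject is eligible for enrollment at Screening". Section 10.1.2.1 lists the blood draw among the Baseline procedures, after Screening, and then says "Following completion of the baseline procedures administer study drug". Screening, Baseline and Day 1 are expected to fall on one date.

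**Eligibility.** The renal criterion in the Synopsis admits clearance below 50 mL/min "as determined by the Cockcroft-Gault formula) including patients on dialysis"; section 8.1 agrees. No exclusion in 8.2 sets a lower limit on clearance.

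**SAP.** Exposure is summarized by age group and overall (5.3.4; Table 14.3.5). Plasma concentrations are summarized by time point and age group (5.2.3; Tables 14.4.1.1 and 14.4.1.2). The baseline characteristics named in 5.1 do not include clearance. Dosing, chemistry, weight and protocol deviations are listed by subject.

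**The concern.** The trial gives one dose, so a wrong dose cannot be corrected at a later visit. The clause that sets the dose needs a creatinine value, while the clause on laboratory timing lets treatment start without one. Subjects aged 65 or over qualify on age alone, so renal impairment need not have been recognised beforehand. The protocol neither reconciles the two clauses nor names a prior or local creatinine value as a substitute, and each site is left to resolve the conflict.

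The primary objective is safety and tolerability in elderly and high-risk subjects, and section 9.8 states that there is no experience of overdose with the intravenous form. If some subjects received more than Table 2 prescribes, or if sites chose different doses below 10 mL/min, the safety results would mix on-table and off-table dosing, and no planned summary would show it.

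A smaller issue affects the descriptive concentration tables. Reduced doses are likely to be more common at older ages, because age lowers the calculated clearance. Pooling doses within age group therefore mixes dose reduction with any effect of age.

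**Working it through.** The plan has no figure of its own to reproduce on this point. The check compares the clauses and then sizes the consequence with the protocol's own equation.

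**1. Does any clause require the result before dosing?** Section 11.2.1 requires the calculation at screening but does not make it a condition for dosing. The Screening list in 10.1.1, the treatment text in 10.1.2 and the Baseline list in 10.1.2.1 contain no clearance step and no wait for a result. In written order, the drug order (end of 10.1.1) precedes the blood draw (10.1.2.1). Footnote 4 permits dosing without results and makes no exception for creatinine.

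**2. Size of a mismatch.** 600/200 = 3; 600/100 = 6. These are dose ratios, not estimates of exposure or harm.

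**3. Creatinine at which the dose should change.** Appendix 1 gives clearance = (140 − age) × weight × (0.85 if female) / (72 × creatinine). Solved for creatinine at clearance c:

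creatinine = (140 − age) × weight × (0.85 if female) / (72 × c)

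The weights are assumed. Example, woman, 80 years, 60 kg, c = 50: 60 × 60 × 0.85 / (72 × 50) = 3060/3600 = 0.85 mg/dL.

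| Subject (assumed) | below 50 if creatinine exceeds | below 30 | below 10 |
|---|---|---|---|
| Woman 60 kg, 65 y | 1.06 mg/dL | 1.77 | 5.31 |
| Woman 60 kg, 80 y | 0.85 | 1.42 | 4.25 |
| Woman 60 kg, 90 y | 0.71 | 1.18 | 3.54 |
| Man 75 kg, 65 y | 1.56 | 2.60 | 7.81 |
| Man 75 kg, 80 y | 1.25 | 2.08 | 6.25 |
| Man 75 kg, 90 y | 1.04 | 1.74 | 5.21 |

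At a creatinine of 1.0 mg/dL the 80-year-old woman has a clearance of 42.5 mL/min, so her Table 2 dose is 200 mg.

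**4. Below 10 mL/min.** The documents give no creatinine range for dialysis subjects; 4 to 12 mg/dL is assumed.

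- Woman, 80 y, 60 kg: 42.5/4 = 10.6 down to 42.5/12 = 3.5 mL/min.
- Man, 65 y, 75 kg: 78.125/4 = 19.5 down to 78.125/12 = 6.5 mL/min.

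Some such subjects fall in the lowest column of Table 2 and others fall below it, where the protocol gives no dose.

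**5. Pooled concentration tables.** Assume peak concentration is proportional to dose and there is no age effect. If a share f of the group aged 65 or over receives 200 mg and the rest 600 mg, the group mean falls by f × (1 − 200/600) = 2f/3:

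- f = 10%: 6.7%
- f = 20%: 13.3%
- f = 30%: 20.0%

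The shares are assumptions. The result is for the peak and does not carry over directly to the later samples.

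**The case against.** The strongest reply is that footnote 4 treats the laboratory panel as a safety baseline and says only that it need not hold up enrolment or treatment. Its wording is permissive and waives neither 9.1 nor 9.4. A compliant path exists: weight and creatinine at screening, clearance calculated under 11.2.1, then an order under 9.3 with its allowance for renal impairment. Medical history and the renal inclusion criterion would catch known impairment. This stands to the extent that the protocol does not instruct anyone to misdose. It does not close the gap for unrecognised impairment, because a site that doses without the result is acting within footnote 4.

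On clearance below 10 mL/min, 9.1 refers to the US package insert, which is not part of the documents, and the last exclusion criterion lets an investigator exclude a subject at unreasonable risk. The gap is narrow, and the number of such subjects is unknown. Even so, the protocol's own text gives no dose to a subject it admits.

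On the SAP, deviations are listed with type and description, so recorded dosing errors would be visible there. Listings are a defensible choice for about 120 subjects in a descriptive study, and no table shells are shown, so Table 14.3.5 may display dose. The population PK model in the Synopsis is meant to identify relevant covariates. These points limit the SAP concern to two things: no planned table sets dose against clearance, so an unrecorded off-table dose is found only by matching listings by hand; and the descriptive concentration tables are not split by dose.

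**Conclusion.** The concern holds in all three parts and should be fixed; confidence in that rating is medium.

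- **Timing.** The dose rule and footnote 4 conflict, and the protocol leaves each site to resolve it. A mismatch would be 3-fold or 6-fold in dose. For the assumed elderly subjects, reduction to 200 mg is called for once creatinine exceeds values between 0.71 mg/dL (woman, 90 y, 60 kg) and 1.56 mg/dL (man, 65 y, 75 kg). The frequency of mismatch is not known.
- **Below 10 mL/min.** Eligible dialysis subjects can have a clearance for which Table 2 gives no dose. This follows from the text; only the illustrative clearances rest on assumed creatinine, age and weight.
- **SAP.** No planned summary shows whether subjects were dosed as Table 2 requires. The pooling effect of 6.7% to 20.0% depends on assumed shares and dose proportionality, and it concerns only the descriptive concentration displays.

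**What to change.** **Protocol.**

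- Exempt creatinine from footnote 4. Require a same-day or recent value, with source and time window set by the sponsor's clinicians, and a calculated clearance before the dose is prepared. Other results may stay pending.
- Add that step to 10.1.1 or 10.1.2.1, and align the footnote in SAP 1.2.
- In 9.4 and Table 2, state a dose or an exclusion for clearance below 10 mL/min, and say explicitly how dialysis subjects are to be dosed.

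The cost is wording in one footnote, one procedure section and one table. Dosing may be delayed at sites without a rapid or recent creatinine value.

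**SAP.**

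- Add one safety-population table of dose received against clearance class: 50 or more, 30 to 49, 10 to 29, and below 10 mL/min or dialysis.
- Present Tables 14.4.1.1 and 14.4.1.2 by dose received within age group.

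The cost is programming one table and splitting two, using age, sex, weight, creatinine and dose, all of which are already collected. Reduced-dose cells may be small.

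**Timing.** The SAP is dated 14 June 2018, and the protocol estimated that the last subject would complete in April 2018. If enrolment has ended, only the SAP changes can still be made.
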